Endometriosis is categorized into three different diseases: peritoneal, ovarian and deep endometriosis.^{3, 4} Peritoneal disease is defined by the presence of superficial peritoneal implants. Ovarian disease includes ovarian surface implants and ovarian endometriomas. Deep endometriosis, on the other hand, involves infiltrative lesions larger than 5 mm in depth affecting the rectovaginal septum, retro-cervical region, sigmoid, rectum, ureter or bladder.⁵ These 3 endometriosis disease types are known to behave and affect women differently - it has been shown that compared to peritoneal and ovarian endometriosis, deep endometriosis is significantly correlated with pelvic pain and infertility.⁶

In 2003, Abrao et al evaluated the histological patterns of endometriosis, observing these histological aspects of the disease: stromal pattern, with the presence of stroma morphologically similar to that of topical endometrium in any phase of the cycle, with no glandular epithelium; well-differentiated glandular pattern, with presence of surface epithelium or epithelium forming glandular or cystic spaces (the morphology of the epithelial cells is indistinguishable from that of topical endometrium during the different phases of the menstrual cycle; undifferentiated glandular pattern, with presence of surface epithelium or epithelium forming glandular or cystic spaces (the epithelium is flattened or low cuboidal, with no correspondence with topical epithelium, resembling the mesothelium lining the peritoneum) and glandular pattern of mixed differentiation with presence of epithelium with a well-differentiated or undifferentiated pattern in the same biopsy. We concluded that the histological classification of endometriosis can predict the prognosis of the disease.

B. Indocyanine Green

In 1958, ICG (Indocyanine Green) was submitted for approval to the FDA for use in indicator-dilution studies in humans. Absorption and fluorescence wave length of IGG lie in the near-infrared (nIR) spectrum. The fluorescence maximum varies with the solvent and lies around 830nm in plasma and 834nm in whole blood. The absorption maximum for blood and plasma is 805nm.

Over the past several years, there has been an explosion of reports describing successful *in vivo* NIR fluorescence imaging. Many studies are qualitative; however, quantitative methods are beginning to emerge where dictated by necessity. Among the clinical applications for ICG fluorescence are:

- Ophthalmic Angiography Studies
- Hepatic Function Studies
- Measurement of Cardiac Output
- Sentinel Lymph Node Diagnosis

[figure not shown]

Figure: Chemical structure of ICG (left) and angiogram of the retina (right)

The endoscopy system described in this document should enable the surgeon to visualize ICG fluorescence in laparoscopic surgery to reach the following goals:

- Detection of ectopic endometrial lesions in the abdominal and pelvic space in the sense of deep infiltrating endometriosis
- Detection of Sentinel Lymph Nodes during tumour resection of cervical or endometrial cancer.

2. Detail description of clinical testing:

a) Near-infrared fluorescence Imaging (NIRF) imaging as a supportive tool for localisation of deep infiltrating endometriosis (DIE) lesions during laparoscopic surgery

Endometriosis is a disease of the uterus in which tissue from the uterine cavity becomes implanted in the abdominal cavity and, rarely, metastasizes to organs at a distance from the uterus. Endometriosis tissue is biologically the same as basal endometrial tissue.

Foci of endometriosis consist of glands, stromal cells, and smooth muscle; they are supplied by nerves (neurogenesis), lymphatic vessels, and blood vessels (angiogenesis).

The diagnosis of endometrial lesions by simple laparoscopic visualization is difficult and often inaccurate.

b) Aim of the Study

Aim of the clinical testing is review the feasibility and potential to establish a new and more accurate method to visualize the peritoneal changes caused by endometriosis by ICG mediated fluorescence imaging. The results and scientific findings obtained within this study shall be used to design a follow-up controlled trial with a higher number of patients.

c) Investigation Points

- Question: Appearance of endometrial lesions and differentiation from surrounding tissue observed in the NIRF image in general
- Hypothesis:
 - It is possible to increase the visual detection rate of peritoneal and deep endometriosis by means of ICG mediated fluorescence.
 - The estimation of extent and size of an endometriotic lesions can be aided by means of ICG mediated fluorescence prior to its excision.
 - Endometriosis of undifferentiated pattern may have different appearance by means of ICG mediated fluorescence than well differentiated and stromal disease

d) Study Design and Study Participants

- Study Participants: Prospective analysis of 25 patients undergoing laparoscopy for suspected endometriosis under white light illumination and ICG imaging diagnosis.
- Inclusion criteria:
 - Suspected endometriosis with necessity for laparoscopic confirmation and resection
 - Regular menstrual cycles
- Exclusion criteria:
 - Patients younger than 18 years and older than 50 years at time of operation
 - Subject has previous history of adverse reaction or allergy to ICG, iodine, shellfish or iodine dyes
 - Documented allergy to sulfur containing compounds
 - History of allergic reactions attributed to compounds of similar chemical or biologic composition to ICG
 - Subject has significant liver disease, cirrhosis or liver insufficiency with abnormal liver function tests (Total bilirubin increased by factor 1.5 than normal and/or serum glutamic oxaloacetic transaminase increased by factor 2 than normal)
 - Subject has uremia, serum creatinine ($> 2.0 \text{ mg/dl}$)
 - Subject has severe coronary heart disease (instable angina pectoris)
 - Pregnant or breast-feeding women

- Subject is actively participating in another drug, biologic and/or device protocol
- The presence of medical conditions contraindicating general anesthesia or standard surgical approaches
- Subject has any medical condition, which in the judgment of the Investigator and/or designee makes the subject a poor candidate for the investigational procedure

e) Procedure:

- Patients are recruited within the clinical routine after indication for laparoscopy under consideration of inclusion and exclusion criteria. After obtaining the patient's consent the patient is included into the study. Withdrawal of the patient from the study is possible at any time without resulting disadvantages or drawbacks in the patient's treatment.
- During the procedure, the sites is initially subjected to visual inspection using direct laparoscope visualization under white light conditions. All areas suspected of peritoneal endometriosis are classified as white, black and red lesions and recorded together with their anatomic location in the surgical record for the purposes of subsequent extirpation. All areas suspected of deep infiltrating endometriosis are recorded together with their anatomic location in the surgical record for the purposes of subsequent extirpation (retrocervical, vaginal, rectosigmoid, bladder lesions)

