## ***Statistical analysis***

Normally the WLy is the gold standard to detect the endometriosis. We test the null hypothesis of identifying occult endometriotic lesions to WLy through the NIR-ICG in about 15% of patients. The sample size was calculated according to the study design by Simon, using an alpha-error of 0.05 and a beta-error of 0.95. Considering a patient dropout of approximately 10%, the study was planned to enrol at least 18 women. Sensitivity, specificity, positive predictive value (PPV), negative predictive value (NPV), and overall accuracy were calculated for each vision mode using standard formulas. Sensitivity was defined as the number of endometriosis who were correctly identified (true positives) divided by the total number of endometriosis (true positives + false negatives). Specificity was defined as the number of negative lesions for endometriosis who were correctly identified (true negatives) divided by the total number of negative lesions (true negatives + false positives). PPV was calculated as the number of true positives divided by the total number of positive results (true positives + false positives), and NPV was defined as the number of true negatives divided by the total number of negative results (true negatives + false negatives).

Accuracy was calculated as the number of true positives plus true negatives (total number correct) divided by the total number of patients studied.

The pretest probability and post-test probability values for WLy and NIR-IGC were also calculated. The 95% confidence intervals were determined for each parameter. Sensitivity, specificity, and accuracy were compared using the McNemar test. The diagnostic performances of WLy and NIR-IGC were calculated on a per-patient as well as on a per-lesion basis considering final pathologic finding.

Receiver operating characteristic (ROC) curve analysis with 95% confidence interval (CI) was used to assess the ability of the ICG-NIR evaluation to identify patients who were most likely to have endometriotic lesion. Statistical calculations were performed using the Statistical Package for Social Sciences (Version 17.0, SPSS Inc., Chicago, IL, USA).

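### The protocol's 25 patients and the SAP's floor of 18 are unreconciled, and no evaluable N or cut-off is fixed for the test against a 15% rate at alpha 0.05

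*Protocol*

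**What the plan says.** Protocol section 2(d), Study Design and Study Participants, gives the size as a "Prospective analysis of 25 patients undergoing laparoscopy for suspected endometriosis under white light illumination and ICG imaging diagnosis". It offers no statistical rationale, dropout allowance or evaluable number.

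The SAP's Statistical analysis section frames a null hypothesis of occult lesions found "through the NIR-ICG in about 15% of patients". It continues: "The sample size was calculated according to the study design by Simon", "using an alpha-error of 0.05 and a beta-error of 0.95". Then, "Considering a patient dropout of approximately 10" per cent, "the study was planned to enrol at least 18 women".

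The SAP gives no alternative rate, stage sizes, interim or final cut-off, or sidedness. It has no rule for applying the test when more than 18 women are enrolled. Neither document mentions the other's number.

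**The concern.** A Simon design is a set of stage sizes and cut-offs, and its error rates belong to those numbers only. An enrolment floor settles how many women to recruit at least. It does not settle how many positive women reject the 15% rate when the cohort is larger. With 25 in one document and 18 as a floor in the other, the evaluable number could be anything from about 16 (18 less dropout) to 25, and the required count changes over that range. Seven positive women would reject 15% at 22 evaluable but not at 25. A reader holding both documents cannot say in advance which result counts as success.

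Protocol section 2(b) says that the findings will be used to design a larger controlled trial, so a false positive on the occult-lesion rate would carry forward.

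**Working it through.** **Inputs.** From the documents: protocol N = 25; SAP enrolment of at least 18; dropout about 10%; null rate p0 = 0.15; alpha = 0.05. Assumed because the documents do not say: a one-sided exact test; power of 0.95 in place of the stated beta (a literal beta of 0.95 means power of 1 − 0.95 = 0.05); alternative rates p1 of 40%, 50% and 55%.

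**1. Can the SAP's 18 be reproduced?** Not strictly, because p1, the stage sizes and the cut-off are missing. It can be reached under assumptions:
- Single stage, p1 = 50%, power 0.95: n = 18, reject at 6 or more (alpha 4.19%, power 95.2%).
- Simon minimax, p1 = 50%, power 0.95: continue if more than 2 of 13, reject if more than 5 of 18 (alpha 4.12%, power 95.0%).
- Simon optimal, p1 = 55%, power 0.95: continue if more than 1 of 7, reject if more than 5 of 18 (alpha 3.48%, power 95.3%).

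All three give 18 before dropout. If 18 already includes dropout, about 16 are evaluable.

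**2. Does dropout link 18 and 25?** Enrolled = evaluable / 0.9.
- 16 / 0.9 = 17.8, so 18 enrolled.
- 18 / 0.9 = 20 enrolled.
- 25 × 0.9 = 22.5, so 22 or 23 evaluable.

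None of these connects the two figures.

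**3. Smallest valid single-stage cut-off at each N.** Choose the smallest r with P(X ≥ r | n, 0.15) ≤ 0.05. Power is P(X ≥ r | n, p1).

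| Evaluable n | Cut-off r | Exact alpha | Power at 40% | Power at 50% |
|---|---|---|---|---|
| 16 | 6 | 2.4% | 67.1% | 89.5% |
| 18 | 6 | 4.2% | 79.1% | 95.2% |
| 22 | 7 | 3.7% | 84.2% | 97.4% |
| 23 | 7 | 4.6% | 87.6% | 98.3% |
| 25 | 8 | 2.6% | 84.6% | 97.8% |

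At 25, a cut-off of 7 would give alpha 6.95%, which is why 8 is needed.

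**4. What if a cut-off built for 18 were kept for a larger cohort?** For the two-stage rules, the first stage and the final cut-off are kept and the second stage is extended.

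| Rule built for 18 | Alpha at 18 | At 22 | At 23 | At 25 |
|---|---|---|---|---|
| Single stage, 6 or more | 4.2% | 10.0% | 11.9% | 16.2% |
| Two-stage, >2/13 then >5 | 4.1% | 8.8% | 10.1% | 12.7% |
| Two-stage, >1/7 then >5 | 3.5% | 7.0% | 8.0% | 10.0% |

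Against the nominal 5%, the single-stage rule gives 10.0 / 5 = 2.0 times at 22 and 16.2 / 5 = 3.2 times at 25. The two-stage rules give 7.0 / 5 = 1.4 times at the low end and 12.7 / 5 = 2.5 times at the high end.

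**The case against.** The strongest reply is that the SAP's figure is a minimum for enrolment after a dropout allowance, not the analysis N of the design. A floor is compatible with a fixed design, and 25 clears it. That stands: a reader might infer a contradiction, but the documents support only a lack of reconciliation. The floor still does not supply the missing cut-off for the larger cohort.

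A reader might also infer that the error rate of this trial is in fact three or four times too high. The documents do not support that. They state no cut-off at all, and nothing says that an 18-patient rule would be applied to 25; a rule matched to 25 (8 or more) has alpha 2.6%. A multiple that large against the nominal 5% also needs a single-stage test with all 25 women evaluable. With 10% dropout, or under the two-stage rules tried, it is smaller.

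Two further inferences fail. The 15% test is not the only formal test, because the SAP also plans McNemar comparisons of sensitivity, specificity and accuracy; it is the test behind the sample size. And neither document describes ending enrolment according to results, so a charge of stopping when the data look favourable would be speculation.

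The power cost of the smaller size depends on the unstated alternative: it is visible at 40% and small between 18 and 25 at 50%. This is also a feasibility study, which limits the consequences.

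**Conclusion.** The point holds in a limited form. The two documents give sizes that nothing reconciles, and the SAP's alpha is attached to no stated N or cut-off for the cohort that the protocol describes. The count needed to reject 15% moves from 6 to 8 across the evaluable numbers that the documents allow. The inflation to about 7–13% (two-stage) or 10–16% (single-stage) is conditional on carrying over an 18-patient rule, and rests on cut-offs derived here under assumed alternatives and a one-sided exact test. It measures what the missing rule could cost, not an error already made. The omission should be corrected because the sample size and the conclusion of the 15% test both rely on it.

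**What to change.** State one enrolled N and one evaluable N, identical in both documents.

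If 25 stands, say in the SAP that 25 women are enrolled and about 22 are expected to be evaluable after 10% dropout. Then do one of the following:
- Give Simon stage sizes and cut-offs recomputed for that evaluable N.
- Say openly that a single-stage exact test replaces the Simon design: reject 15% if 7 or more of 22 evaluable women have an occult lesion found by NIR-ICG (exact one-sided alpha 3.7%), with the exact binomial test against 15% at one-sided 0.05 for any other evaluable number.

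If 18 stands, change protocol section 2(d) to match. Say whether 18 is the enrolled number (about 16 evaluable) or the evaluable number (20 enrolled), and give the cut-offs for it.

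In either case, state the sidedness, name the alternative rate and the power at that rate, and correct "a beta-error of 0.95" so that beta and power are not confused.

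No extra patients are needed. The work is a short edit to the SAP paragraph and, if 18 is kept, to the protocol line. The only cost is that a stated alpha or power figure may look slightly less favourable once it is tied to a real cut-off.

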## ***Statistical analysis***

Normally the WLy is the gold standard to detect the endometriosis. We test the null hypothesis of identifying occult endometriotic lesions to WLy through the NIR-ICG in about 15% of patients. The sample size was calculated according to the study design by Simon, using an alpha-error of 0.05 and a beta-error of 0.95. Considering a patient dropout of approximately 10%, the study was planned to enrol at least 18 women. Sensitivity, specificity, positive predictive value (PPV), negative predictive value (NPV), and overall accuracy were calculated for each vision mode using standard formulas. Sensitivity was defined as the number of endometriosis who were correctly identified (true positives) divided by the total number of endometriosis (true positives + false negatives). Specificity was defined as the number of negative lesions for endometriosis who were correctly identified (true negatives) divided by the total number of negative lesions (true negatives + false positives). PPV was calculated as the number of true positives divided by the total number of positive results (true positives + false positives), and NPV was defined as the number of true negatives divided by the total number of negative results (true negatives + false negatives).

Accuracy was calculated as the number of true positives plus true negatives (total number correct) divided by the total number of patients studied.

The pretest probability and post-test probability values for WLy and NIR-IGC were also calculated. The 95% confidence intervals were determined for each parameter. Sensitivity, specificity, and accuracy were compared using the McNemar test. The diagnostic performances of WLy and NIR-IGC were calculated on a per-patient as well as on a per-lesion basis considering final pathologic finding.

Receiver operating characteristic (ROC) curve analysis with 95% confidence interval (CI) was used to assess the ability of the ICG-NIR evaluation to identify patients who were most likely to have endometriotic lesion. Statistical calculations were performed using the Statistical Package for Social Sciences (Version 17.0, SPSS Inc., Chicago, IL, USA).

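### The SAP sizes the study on the share of patients with lesions occult to white light (about 15%), but no listed analysis estimates or tests that share, and the Simon rule cannot be recovered

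*SAP*

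**What the plan says.** The SAP (Statistical analysis) states one hypothesis, at patient level: "We test the null hypothesis of identifying occult endometriotic lesions" to white light (WL) "through the NIR-ICG in about 15% of patients". On sizing it says: "The sample size was calculated according to the study design by Simon, using an alpha-error of 0.05 and a beta-error of 0.95". It continues: "Considering a patient dropout of approximately 10%, the study was planned to enrol at least 18 women".

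The analyses listed after that are sensitivity, specificity, PPV, NPV and accuracy for each vision mode, pretest and post-test probabilities, and a ROC curve. Two sentences could be thought to cover the hypothesis: "The 95% confidence intervals were determined for each parameter" and "Sensitivity, specificity, and accuracy were compared using the McNemar test". Diagnostic performance is to be calculated "on a per-patient as well as on a per-lesion basis considering final pathologic finding".

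The protocol (2 d, Study Design and Study Participants) plans 25 patients and gives no sample-size calculation. Its Procedure (2 e) collects what the share would need. At the first WL inspection, "All areas suspected of peritoneal endometriosis are classified as white, black and red lesions and recorded together with their anatomic location"; suspected deep lesions are likewise recorded by site. Areas suspect under ICG are then recorded with their WL appearance, and areas suspect in either mode are sampled.

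**The concern.** A study sized on a one-sample hypothesis about a proportion should report that proportion, an interval for it, and the rule by which the hypothesis is judged. The visible SAP lists none of these. Followed as written, the report would contain accuracy measures and McNemar p-values, but no figure for the quantity that set the sample size and no pre-specified conclusion about 15%.

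The protocol (2 b, Aim of the Study) says the results will be used to design a larger controlled trial. The share of women in whom ICG adds a confirmed lesion, with its uncertainty, is a natural input to that design. If the rule is chosen only after the counts are known, the choice can decide the answer.

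**Working it through.** **Inputs.** From the SAP: rate about 0.15 at patient level; alpha 0.05; a beta-error of 0.95; dropout about 10%; at least 18 women. From the protocol: 25 patients. Not stated: the alternative rate, optimal or minimax, stage sizes, cut-offs and sidedness. Assumptions used below: 15% is the rate to be rejected, the test is one-sided, and alternative rates are as labelled.

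**1. Can the 18 be reproduced?** Not uniquely. Read literally, a beta-error of 0.95 means 5% power; presumably power of 0.95 was meant. With a null of 0.15, alpha 0.05 and an assumed alternative of 0.50:

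| Design | Stop at stage 1 if | Reject if | Alpha | Power | After dropout |
|---|---|---|---|---|---|
| Optimal, 80% power | ≤1 of 5 | ≥5 of 16 | 0.045 | 0.800 | 16/0.9 = 17.8, so 18 |
| Minimax, 95% power | ≤2 of 13 | ≥6 of 18 | 0.041 | 0.950 | 18/0.9 = 20 |

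The first gives 18 after dropout and the second 18 before it, with different cut-offs. The choice matters: 5 of 16 rejects under the first design (if stage 1 was passed), while a single-stage exact test gives P(Bin(16, 0.15) ≥ 5) = 0.079.

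**2. Do the listed analyses give the share?**
- The sentence on confidence intervals refers to the listed parameters, and the share is not among them.
- McNemar's null is that the two kinds of discordance are equally likely; 15% does not enter it. Per patient, a woman with one confirmed WL-positive lesion and another confirmed NIR-only lesion is positive in both modes, so she is concordant. She is nevertheless an occult case.
- Per-lesion results can show NIR-only lesions, but not how many women they come from.

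**3. How far can McNemar and the binomial test diverge?** The counts are constructed. Exact two-sided McNemar with k discordant patients all one way is p = 2 × 0.5^k.
- 18 women, 9 with an occult lesion, 4 of these also WL-positive, none WL-only. Binomial: P(Bin(18, 0.15) ≥ 9) = 0.0005. Per-patient McNemar, k = 9 − 4 = 5: 2 × 0.5^5 = 0.0625.
- 25 women, 6 NIR-only, no other occult patients, none WL-only. McNemar, k = 6: 2 × 0.5^6 = 0.031. Binomial: P(Bin(25, 0.15) ≥ 6) = 0.16; the share is 24%, exact 95% interval 9% to 45%.

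**4. What would a single-stage test require?** The cut-off is the smallest c with P(Bin(n, 0.15) ≥ c) ≤ 0.05. The 16 is 18 less about 10% (18 × 0.9 = 16.2).

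| n | Reject at | p at cut-off | p one below | Exact two-sided 95% interval at cut-off | One-sided 95% lower limit | Power if share 50% / 40% |
|---|---|---|---|---|---|---|
| 16 | 6 | 0.024 | 0.079 | 0.152 to 0.646 | 0.178 | 0.895 / 0.671 |
| 18 | 6 | 0.042 | 0.121 | 0.133 to 0.590 | 0.156 | 0.952 / 0.791 |
| 25 | 8 | 0.025 | 0.070 | 0.1495 to 0.535 | 0.170 | 0.978 / 0.846 |

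At 6 of 18 and 8 of 25 the two-sided interval includes 0.15 although the one-sided test rejects. The one-sided lower limit therefore has to be reported with the test.

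**The case against.** **The hypothesis sentence is garbled.** The 15% may be an expected or target rate mislabelled as a null. Under that reading, 18 women give a probability of 1 − 0.85^18 = 0.946 of seeing at least one occult patient. The fit is inexact (0.926 with 16 evaluable), so this is only a possibility, but it stands: the cut-offs above apply only if 15% is to be rejected. The missing estimate is a gap under either reading.

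**McNemar was never assigned to the 15%.** True: the SAP assigns it to sensitivity, specificity and accuracy. The contrast shows only that it cannot fill the gap. The first example is also specific to the per-patient analysis. Nine occult women mean at least nine NIR-only lesions; with no WL-only lesions, an unclustered per-lesion McNemar gives p ≤ 2 × 0.5^9 = 0.004. Even so, that result does not give a share of patients.

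**Naming Simon supplies the rule.** It supplies a type of rule. Some candidates near 18 do agree: the single-stage tests at 16 and 18 and the 95%-power minimax design all reject at 6. The 80%-power design rejects at 5 of 16, so the rule is still not unique.

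**This is a feasibility study, and the data are collected anyway.** The documents tie no go/no-go decision to 15%, and the share could be tabulated from the planned records. This lowers the severity but does not remove the gap, since the SAP itself chose a formal hypothesis with alpha and power.

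**Conclusion.** The point holds for the visible text. The Statistical analysis section sizes the study on a patient-level share and lists no estimate, interval or test of it. The Simon rule cannot be reconstructed, and designs at or near 18 women have different cut-offs. This should be fixed, but it is not fatal to a feasibility study.

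A reader might infer more than the documents support:
- *That 18 is wrong.* The calculation does not show this; the alternative rate is missing, and 18 is compatible with more than one design.
- *That 15% is certainly the rate to be rejected.* The wording does not settle it.
- *That the share is defined nowhere in the SAP.* Other parts of the SAP were not available for review, so the absence is established only for this section and the protocol text supplied.
- *That the study cannot answer the question.* The protocol's records largely allow it; what is missing is the counting rule and the analysis.

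The numerical illustrations rest on a one-sided alpha of 0.05, on 15% as the null, on reading the beta-error as power where 0.95 is used, and on assumed alternative rates and counts.

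**What to change.** 1. State whether 15% is the rate to be rejected or the expected rate, and correct the beta-error of 0.95.
2. Make the primary analysis the proportion of patients imaged in both modes who have at least one pathology-confirmed lesion that was conspicuous under ICG and not recorded as suspect at the first WL inspection. Use this one definition for peritoneal and deep lesions. Add a sensitivity analysis restricted to areas that look inconspicuous in WL.
3. Report the share with an exact 95% interval.
4. If 15% is the null, test it by a Simon rule with its alternative rate, design type, stage sizes and cut-offs written out. If the study is single-stage, use an exact binomial test at one-sided 0.05 (sidedness to be confirmed), rejecting at ≥6 of 16, ≥6 of 18 or ≥8 of 25, with the matching one-sided lower limit.
5. Keep McNemar as secondary, with its unit (patient or lesion) stated.

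**Cost.** One SAP paragraph, plus a rule for matching each ICG area to the first WL record. The WL record, the WL appearance of ICG areas and the excisions are already in the protocol's Procedure. The SAP section is written in the past tense; if data are already in hand, the test should be labelled post hoc.

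### The SAP states a beta-error of 0.95 (literally 5% power) and omits the alternative rate and cut-off, so the 18 women cannot be reproduced or read as 95% power for a known effect

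*SAP*

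**What the plan says.** All of the sample-size reasoning in the visible text is in the SAP, Statistical analysis:

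- **Hypothesis.** "We test the null hypothesis of identifying occult endometriotic lesions to" white light "through the NIR-ICG in about 15% of patients". One rate is given, and it is attached to the word null.
- **Design and error rates.** "The sample size was calculated according to the study design by Simon, using an alpha-error of 0.05 and a beta-error of 0.95".
- **Size.** "Considering a patient dropout of approximately 10%, the study was planned to enrol at least 18 women".
- **Analyses.** The section lists sensitivity, specificity, PPV, NPV, accuracy, pre-test and post-test probability, and a ROC curve. It adds "The 95% confidence intervals were determined for each parameter" and "Sensitivity, specificity, and accuracy were compared using the McNemar test".

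The protocol, section 2 d), plans a "Prospective analysis of 25 patients undergoing laparoscopy for suspected endometriosis" without a calculation. Section 2 b) says that the results "shall be used to design a follow-up controlled trial with a higher number of patients".

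**The concern.** There are three linked faults.

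1. **The stated error rate is wrong as written.** A beta of 0.95 is a 95% chance of missing the effect. Nobody plans for that, so the figure was probably meant as power.
2. **The calculation lacks inputs.** A Simon design needs a null rate, an alternative rate, alpha, beta, and stage sizes with boundaries. Only one rate and alpha can be used as they stand. Correcting beta alone does not bring back the 18.
3. **The stated hypothesis has no listed analysis.** It concerns the share of women in whom NIR-ICG finds disease that white light missed. That share is not among the listed outputs, and no count of such women has a stated reading.

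The stake is interpretation. Someone who reads the sentence as 95% power will suppose that the study could reliably show a worthwhile excess over 15%. Whether it could depends on an alternative rate that is not given. The designers of the follow-up trial need to know which rates this study could distinguish from 15%.

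**Working it through.** **Inputs from the SAP.** Null rate p0 = 0.15; alpha = 0.05; dropout about 10%; enrolment at least 18.

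**Assumptions, because the SAP is silent.** 0.95 is read as power; alpha is one-sided (an upper tail of 0.025 is also tried); the test is exact binomial; dropout is applied as n/0.9, rounded up.

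**Step 1: try to reproduce 18.** Without an alternative rate p1 there is no calculation to repeat. Three checks show how far the other inputs go.

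- *Beta taken literally.* With alpha 0.05 and only 5% power required, 2 to 6 women are enough for any p1 from 0.16 to 0.50. The printed figure does not lead to 18.
- *0.95 read as power, single stage.* The smallest n and the enrolment n/0.9 are:

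| p1 | n | enrol |
|---|---|---|
| 0.30 | 85 | 95 |
| 0.40 | 33 | 37 |
| 0.45 | 26 | 29 |
| 0.50 | 18 | 20 |
| 0.55 | 14 | 16 |

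- *0.95 read as power, Simon two-stage.* Optimal and minimax designs were searched for p1 from 0.48 to 0.62 in steps of 0.01. After n/0.9, none gives 18; the nearest give 17 and 19. At p1 = 0.50 the minimax design has a maximum of 18 women (stop at 2 or fewer of 13; reject at 6 or more of 18), but that leaves no dropout allowance. At 80% power and p1 = 0.50 the optimal design has 16 women, and 16/0.9 = 17.8 rounds up to 18. This does not show that such a design was used. It shows that different inputs can lead to 18.

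**Step 2: what 16 to 18 evaluable women can show.** Enrolling 18 and losing 10% leaves 18 × 0.9 = 16.2, so about 16. The cut-off r is the smallest count with P(X ≥ r | n, 0.15) ≤ alpha. Power is P(X ≥ r | n, p1).

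For n = 16, P(X ≥ 5 | 0.15) = 0.079, which is too large, and P(X ≥ 6 | 0.15) = 0.0235. So r = 6. Power is then P(X ≥ 6 | 0.30) = 0.340 and P(X ≥ 6 | 0.40) = 0.671. It reaches 0.95 at p1 = 0.548.

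| Evaluable | Reject at | Actual alpha | Power at 30% | Power at 40% | 95% power at |
|---|---|---|---|---|---|
| 16 | ≥6 | 0.024 | 34% | 67% | 55% |
| 17 | ≥6 | 0.032 | 40% | 74% | 52% |
| 18 | ≥6 | 0.042 | 47% | 79% | 50% |

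With an upper tail of 0.025 the cut-offs are 6, 7 and 7, and 95% power is reached at 55%, 58% and 55%.

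**Step 3: the protocol's number, for scale.** If 25 are enrolled and the SAP's 10% loss is applied, 25 × 0.9 = 22.5, so about 22. Neither document states this combination. The cut-off is ≥7 (alpha 0.037); power is 51% at 30% and 84% at 40%, and 95% is reached at 47%.

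**Step 4: compare the hypothesis with the outputs.** The promise of confidence intervals covers the listed parameters, and the NIR-only rate per woman is not one of them. McNemar uses the discordant results but tests whether the two modes differ, not whether the NIR-only share exceeds 15%.

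**The case against.** **It is one wrong word.** The beta figure may well be no more than that. Correcting it still leaves the alternative rate, sidedness, boundaries and the test itself unstated.

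**No arithmetic in the SAP is shown to be wrong.** This stands. A reader might infer that 18 is a miscalculation or that the study was planned at 5% power. The documents support neither: 18 roughly fits an alternative near 50-55%, and the Simon search in Step 1 rests on an assumed one-sided alpha and an assumed dropout formula.

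**A feasibility study need not be powered.** True in general, and designers of the next trial will lean more on the observed rate and its interval than on power. But the SAP chose a hypothesis, error rates and a Simon design, and it does not list that rate or its interval.

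**Discordance is already analysed by McNemar.** In part. That narrows the gap but does not close it (Step 4).

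**15% may be the target.** The SAP's word is null, so that is the working assumption. If 15% was the target, the probability of seeing at least one such woman is 1 − 0.85^18 = 0.946 with 18, or 0.926 with 16. That is close to 0.95, so the SAP should say which was meant.

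**A tempting overstatement.** A reader might take a non-significant result as evidence that NIR-ICG adds nothing. It would not be. A 15% NIR-only rate is itself detection beyond white light; failing to reject means only that a rate above 15% was not shown.

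**The inputs may be elsewhere.** Some pages of both documents were not available for this review, so what is said to be missing is missing from the visible text only. The printed beta is wrong regardless.

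**Conclusion.** The point holds in a limited form. The printed beta-error is wrong as written, the size of 18 cannot be reproduced from the visible text, and the rate named in the hypothesis has no listed test or interval.

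If 0.95 was meant as power and 15% is the null, 16 to 18 evaluable women have 95% power only for large excesses: a true rate of about 50-55% with one-sided alpha 0.05, or about 55-58% with an upper tail of 0.025. At the SAP's minimum, a doubling of the null rate to 30% would go unshown 66% of the time (100 − 34). These figures assume an exact binomial test, and sidedness is not stated.

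This should be fixed, but it does not invalidate the study. It limits what a reader may conclude from the power statement.

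**What to change.** In the SAP, Statistical analysis:

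1. Correct the beta-error to the intended value (0.05 if 95% power was meant).
2. Confirm whether 15% is the null or the target, and state the other rate actually used.
3. State sidedness and the Simon stages and boundaries used, or call it a single-stage exact test.
4. Add the per-patient rate of pathology-confirmed NIR-only disease to the outputs, with an exact 95% confidence interval.
5. Reconcile 18 (SAP) with 25 (protocol), then restate power as detectable rates for the number actually used. Label these as such, not as the original rationale.
6. The section is written in the past tense. If the original cut-off cannot be recovered, label any cut-off supplied now as not prespecified.

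The cost is a few sentences, with no extra patients and no change to procedures. The downside is that the stated power will look less favourable.
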